## **6.1 Blinding**

All study subjects and Study Team members responsible for subject evaluation, data management and analysis (Including the Principal Investigator) will be blinded to treatment through 18 months follow-up. In addition, any individuals engaged by the Principal Investigator to provide of radiographic, laboratory testing and and/or verification of data will be blinded to treatment.

One Study Team Member responsible for group assignment, the pharmacist responsible for medication distribution and the Independent Medical Monitor will be unblinded.

---

## **7.0 Study Medication Treatment**

### **7.1 Losartan Potassium**

Losartan potassium is an angiotensin II receptor (type AT1) antagonist. Losartan potassium, a non-peptide molecule, is chemically described as 2-butyl-4-chloro-1- [p-(o-1H-tetrazol-5-ylphenyl)benzyl]imidazole-5-methanol monopotassium salt. Losartan potassium is a white to off-white free-flowing crystalline powder with a molecular weight of 461.01. It is freely soluble in water, soluble in alcohols, and slightly soluble in common organic solvents, such as acetonitrile and methyl ethyl ketone. Oxidation of the 5-hydroxymethyl group on the imidazole ring results in the active metabolite of losartan.

Losartan will be sourced through PenCol Compounding Pharmacy, located in Denver, Colorado. provided to subjects in its approved, marketed generic form. Scored tablets containing 25 mg of active ingredient (losartan) will be split by the pharmacy to provide individual dosage of 12.5 mg, to be taken by subjects twice daily (BID). Directions for Use can be found in using the following link.

<https://www.bioportfolio.com/resources/drug/15151/Losartan-Potassium-Sandoz-Inc.html>

---

### **7.2 Placebo Control**

Appearance matched placebo medication will also be compounded at PenCol Compounding Pharmacy, located in Denver, Colorado.

### **7.3 PenCol Compounding Pharmacy**

PenCol is accredited by the Pharmacy Compounding Accreditation Board (PCAB). This accreditation confers the most comprehensive compliance assurance in the pharmaceutical industry, with standards based on U.S. Pharmacopeial Convention (USP) guidelines. This process includes an extensive on-site survey conducted by an independent expert and annual verification ensures compliance with the non-sterile and sterile pharmacy compounding process defined by USP <795> and USP <797>. The address and contact information for PenCol is provided below.

[name]  
[name]  
[name]  
[contact]

The compounding pharmacy will work directly with the Vail Pharmacy within Vail Health Hospital. All subjects will obtain their medication (or placebo) directly from Vail Pharmacy.

---

**Clinical Protocol No. 2019-15**

**Version 001**

**Page 18 of 58**

---

**8.0                    Study Design**

This is a prospective, randomized, placebo controlled, double blind study. to be conducted at the Steadman Clinic and the Steadman Pilippon Research Institute. A total of 40 subjects will be randomized 1:1 to receive either standard microfracture of the hip + losartan or standard microfracture of the hip + placebo.

Subjects will be blinded to medication treatment. To maximize the objectivity of follow-up evaluations, all Study Team members involved in study assessments or documentation will be blinded through 18 months follow-up.

## **9.0 Study Objectives and Endpoints**

### **9.1 Primary Objectives**

#### **To evaluate:**

1. Cartilage quality as assessed by quantitative MRI at 18 months postoperatively compared between patients treated with losartan + microfracture and microfracture + placebo alone;
2. The safety of administering losartan in conjunction with microfracture surgery.

### **9.2 Secondary Objective**

#### **To evaluate:**

1. Patient reported outcomes at 3, 6, 12, and 18 months postoperatively compared between patients treated with losartan + microfracture and microfracture alone (placebo).

### **9.3 Study Endpoints**

#### **9.4 Primary Endpoints:**

1. T2 mapping values and texture analysis metrics for quantitative MRI mapping;
2. Occurrence of adverse events.

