At the conclusion of study medication, subjects will be contacted by the Study Team to confirm completion of medication. The occurrence protocol deviations and of all adverse events will be documented.

At three months post operatively, subjects will be seen for a visit The Steadman Clinic. A copy of the Medication Log will be retained by the Study Team, and subjects will complete Patient Reported Outcomes (PROs) either on paper or electronically. These tools are described in more detail in [Section 13.5](#) of this protocol. All medical history will be updated including all medications. Vital signs will be recorded, and subjects will undergo strength testing and range of motion assessment by the Principal Investigator or a designee. Protocol deviations and all adverse events related to the target hip will be collected.

At six and twelve months post operatively, subjects will be required to complete from home the assigned PROs electronically. Subjects will be contacted by phone and protocol deviations and all adverse events related to the target hip will be collected.

At eighteen months postoperatively, subjects will be seen at the Steadman Clinic. PRO questionnaires will be completed. Medical history will be updated including all medications. Vital signs will be recorded, and subjects will undergo strength testing and range of motion assessment by the Principal Investigator or a designee. In addition, morphological and quantitative T2 MRI will be performed to assess the regrowth of new cartilage tissue. protocol deviations and all adverse events related to the target hip will be collected.

After all subjects have reached 18 months follow-up, primary and secondary outcomes will be analyzed as described in [Section 17](#) of this document. Unblinding of the Study Team and the Subject will occur.

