**15.0 Statistical Considerations**

Patients will be randomized with a 1:1 allocation ratio into either the microfracture plus losartan versus microfracture alone group. Block randomization will be used with block sized of n=8 to ensure that groups are of approximately equal size at study completion, even if some patients are lost to follow-up or unenrolled.

Intent-to-treat analysis will be performed. We will compare group means, with the hypothesis that greater post-operative PROs and higher graft quality as assessed with quantitative imaging will be observed in the microfracture plus losartan group compared to microfracture alone. Analysis of Covariance (ANCOVA) or Linear mixed-effect models with random intercepts will be used to compare groups while adjusting for the baseline measurement of each subject.

The effect size of microfracture plus losartan compared to microfracture alone with respect to patient reported outcomes is unknown, so a sample size calculation was performed based on anticipated quantitative

Anticipated effect sizes for the group difference with respect to MRI-assessed cartilage quality were derived from the literature, however a paucity of helpful literature was found in the hip literature. Sample size for this study was determined via a statistical power analysis using published data from Apprich, et al , who compared patients treated with microfracture of the talus versus patients treated with matrix-associated autologous chondrocyte transplantation (MACT).

The primary outcome metric reported in Apprich, et al was a semi-quantitative scale of diffusion-weighted imaging (DWI) acquired by MRI and the paired differences between DWI of the repaired tissue and healthy reference cartilage for each patient was reported for each treatment group. We aim to power this study to detect an effect size between the microfracture alone and microfracture plus losartan groups that is equal to the observed between-group effect size calculated from Apprich, et al (d=1.107).

The significance level will be set at  $\alpha=0.05$ . Assuming 2-tailed testing and requiring 90% statistical power, 19 patients per group are sufficient to detect the effect size of interest. We aim to enroll 20 subjects per group. Power calculations were performed using G\*Power (version 3.1; Universität Düsseldorf).

---

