**17.0      Disclosure and Confidentiality**

By signing the protocol, the Principal Investigator agree to keep all study documents in strict confidentiality and to request similar confidentiality from his/her staff and the Institutional Review Board. study documents (Protocols, and other material) will be stored appropriately to ensure their confidentiality.

---

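### The primary MRI endpoint is several unlisted T2 and texture metrics, but the 0.05 level and 90% power in Section 15.0 fit one unnamed comparison

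*Combined protocol and SAP*

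**What the plan says.** Section 9.4 and the synopsis give the first primary endpoint in the same words: "T2 mapping values and texture analysis metrics for quantitative MRI mapping". Both parts are plural, and neither place says how many metrics there are or which one leads. Section 9.1 fixes the time point (18 months) and speaks of cartilage quality on quantitative MRI. Section 15.0 states the hypothesis as "higher graft quality as assessed with quantitative imaging". It plans an intent-to-treat comparison of group means by ANCOVA or a mixed model, "adjusting for the baseline measurement of each subject", and names no imaging variable for the model.

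On size, Section 15.0 sets alpha at 0.05 and continues: "Assuming 2-tailed testing and requiring 90% statistical power, 19 patients per group are sufficient to detect the effect size of interest". Enrolment is 20 per group. The effect size, d=1.107, comes from a published study of the talus whose outcome was "a semi-quantitative scale of diffusion-weighted imaging (DWI) acquired by MRI". No success rule and no allocation of alpha among metrics is given.

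**The concern.** A significance level and a power belong to a defined test on a defined variable. Here the endpoint is a set of metrics, while the error rate and power are stated once. Two competent analysts could each follow the text and report different primary results from the same 40 patients, one on a T2 value and one on a texture feature. If each metric is compared at 0.05 and whichever separates is reported as the primary finding, the 5% no longer describes the chance of a false claim.

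The power has a related gap. The 90% depends on an effect size measured on a scale that is neither T2 nor texture, so it attaches to no endpoint of this trial until a metric is named and the effect size is argued for that metric.

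**Working it through.** **Inputs.** From Section 15.0: d=1.107, two-sided alpha 0.05, power 90%, 1:1 allocation, 19 per group needed and 20 enrolled. The number of metrics k and their correlation are not in the documents. I assume k = 2, 3, 5 or 10, and correlations of 0.9, 0.7 and 0.

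**1. Reproducing the plan's figure.** For a two-sample t-test with n per group, the noncentrality is d·√(n/2) on 2n−2 degrees of freedom.

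- n=18: 1.107·√9 = 3.321, power 89.7%
- n=19: 1.107·√9.5 = 3.412, power 91.3%
- n=20: 1.107·√10 = 3.501, power 92.7%

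Nineteen is the smallest n that reaches 90%. The stated size is therefore correct for one two-sided test at the full 0.05.

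**2. Any one metric counts, each at 0.05.** If the metrics are independent, the chance of at least one false positive is 1−0.95^k. For correlated metrics I use simulated trials (100,000 per case, equally correlated normal metrics, 20 per group, unadjusted t-tests).

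| Assumed k | Correlation 0.9 | Correlation 0.7 | Independent |
|---|---|---|---|
| 2 | about 7% | about 8% | 9.75% |
| 3 | about 8% | about 11% | 14.3% |
| 5 | about 10% | about 15% | 22.6% |
| 10 | about 13% | about 22% | 40.1% |

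Metrics from one scan are probably correlated, so the left-hand columns are the more plausible ones.

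**3. Splitting alpha instead.** With Bonferroni, d=1.107 on every metric and 20 per group, the power for each metric is 87.3% at 0.05/2 and 83.5% at 0.05/3.

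**4. One named metric with a different effect size.** Unadjusted test, alpha 0.05, 20 per group:

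| d | Power |
|---|---|
| 1.107 | 92.7% |
| 1.0 | 86.9% |
| 0.9 | 79.2% |
| 0.8 | 69.3% |
| 0.6 | 45.6% |

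**5. Baseline adjustment.** ANCOVA with baseline correlation r multiplies the standardised effect by about 1/√(1−r²), with 37 degrees of freedom. At d=0.8 the power is 69.3% at r=0, 71.0% at r=0.2 and 81.2% at r=0.5. The documents give no value of r. The preoperative scan is taken before repair tissue exists, so a high r cannot be presumed.

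**The case against.** Several points on the other side have force.

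- **The text may be incomplete.** In Section 15.0 the sentence that introduces the sample size breaks off just where a quantity could have been named. This may be a loss in reading the file and is not counted as a fault. The next paragraph, however, refers only to cartilage quality assessed by MRI, so the readable text still names no metric.
- **The region may be defined elsewhere.** Section 11.8 cites a specific imaging protocol. A reader might infer that no region of interest exists. The documents show only that it is not given here.
- **Silence is not a plan to test everything.** A reader might infer that the sponsor intends to test every metric at 0.05 and claim any win. Section 15.0 does not say so. The error rates above are what follows if that is done; they do not describe a stated rule.
- **The cross-reference is weak evidence.** Section 6.0 says "primary and secondary outcomes will be analyzed as described in" Section 17, which is "Disclosure and Confidentiality". A reader might infer that the primary analysis was never written. Other pointers are off by two in the same way (15.1 for 13.1), and Section 15.0 does contain the statistics. This is a numbering slip to correct editorially, and the point does not rest on it.
- **The study is small and exploratory.** Section 5.1 says so and disclaims any labelling purpose. This limits the consequence. It does not remove the need for a variable, since the plan chose a primary endpoint, an alpha and a power.

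**Conclusion.** The point holds in this form: the primary MRI endpoint is plural and unlisted, and the single 0.05 and 90% are tied to no named metric of the trial. If each metric is compared at 0.05 and any one counts, the error is above 5% in every case examined, from about 7% (two metrics, correlation 0.9) to 40.1% (ten independent metrics). Those figures rest on an assumed number of metrics and assumed correlations, and the upper end should not be read as an estimate for this trial.

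It would go too far to conclude that the trial is underpowered or that 19 per group was miscalculated. The arithmetic is right for one test at d=1.107. What is unsupported is the link between that effect size and a T2 or texture metric. Naming one metric restores the 5%; it does not by itself secure the 90%.

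The 18-month time point, the intent-to-treat principle and baseline adjustment are already fixed. Given the exploratory purpose, this is a should-fix.

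**What to change.** Amend before unblinding, with the same text in the synopsis, 9.4 and 15.0.

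1. **Name one primary MRI variable**, for example mean T2 of the repair region at 18 months. Take its region from the imaging protocol cited in Section 11.8, or add it there. Test it once at two-sided 0.05 by ANCOVA with a named preoperative T2 covariate that can be measured in all patients. Report the other T2 and texture metrics as secondary, with estimates and confidence intervals. **Alternatively**, keep a short named list as co-primary, state a multiplicity adjustment, and restate the power as in step 3 of the working.
2. **Make the power statement conditional.** Say in 15.0 that the 90% holds only if d=1.107 applies to the named metric. Show power over a range of d, and note that any gain from baseline adjustment depends on an unknown correlation.

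The Section 17 pointer in 6.0 can be corrected to Section 15 at the same time.

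The cost is an amendment, agreement with the imaging readers on the region and covariate, and a short power table. No extra patients, scans or visits are needed. The downside is that a single T2 primary may miss an effect that shows mainly in texture. Splitting alpha avoids this but lowers the power for each metric. The stated power may also read below 90%.

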#### **9.5 Secondary Endpoints**

1. Descriptive quantification of patient reported outcomes in each treatment group.  
Investigators and Study Sites

---

## **10.0 Study Population**

Patients who have undergone microfracture for a focal chondral defect of the femoral head or acetabulum will be considered candidates for enrollment. A member of the Study Team will review the patients' standard of care record to determine if all inclusion/exclusion criteria are met. Patients meeting the study's inclusion/exclusion criteria will then be approached by this same study member with the opportunity to provide informed consent to enter this study. This meeting will take place during the patient's first post-operative physical therapy visit in a private setting.

### **10.1 Description**

Qualified subjects who personally give informed consent will be screened for eligibility. Only subjects who meet all eligibility criteria will be randomized and treated with either losartan or placebo.

### **10.2 Source of Subjects**

Study subjects will be identified and recruited from the practice of the Principal Investigator. No external recruitment or advertising is to be engaged.

### **10.3 Enrollment Criteria**

#### **10.3.1 Inclusion Criteria**

Patients who:

1. Are aged 18-60 at time of surgery;
2. Tonnis grade 1 or less;
3. Present with a single, localized, grade 3 or 4 cartilage lesion of the acetabulum or femoral head treated with primary BMS (microfracture) performed by [name].

#### **10.3.2 Exclusion Criteria**

Patients who are

##### **General**

1. Non-English speaking;
2. Diagnosed with inflammatory arthritis or other arthritis caused by autoimmune disease;
3. Taking losartan;
4. Allergic to any active or inactive ingredient of losartan;
5. Taking medication with known losartan interaction'
6. Are hypotensive as confirmed by the surgical anesthesiologist;

**Concerning the target hip have on preoperative assessment:**

7. Prior hip surgery;
8. Two or more cartilage lesions of grade 3 or 4;
9. Less than 2 mm of minimal hip joint space;
10. Osteoarthritis or diffuse change of cartilage;
11. Pre-existing bony deformity caused by previous fracture(s);
12. Synovial chondromatosis;
13. Pigmented Villanodular Synovitis (PVNS);
14. Dysplasia (center edge angle <20 degrees);
15. Coxa profunda;
16. Protrusia Acetabuli.

---

## **11.0      Study Procedures**

Patients who present for treatment and in whom operative treatment has been planned, will as part of their pre-operative evaluation undergo a standard of care medical review. Basic demographic data will be collected, including age, gender, body mass index, chronicity of the injury, and surgical data will be queried. Additional data including medical co-morbidities, smoking status, medication use, will be collected. History of hip trauma, range of motion, strength, size of the cartilage lesion, circumduction evaluation exercises and range of motion restrictions will be evaluated. As standard of care, patients complete several Patient Reported Outcomes (PRO) tools which will be repeated, at key study intervals as described in the following section of this document, should the patient consent to participate in the study. Subjects will also undergo a T2 MRI of the hip as standard of care diagnosis.

These routine baseline measurements will be used to evaluate preliminary eligibility. If eligibility seems likely, a member of the Study Team will briefly describe this study and gauge the patient's interest in participation.

A full Study Schemata is provided in [Appendix B](#).

### **11.1 Visit 1: Day 1 Post-operative**

Each potential subject will be fully informed of all requirements of participation as well as the voluntary nature of participation. If they are interested in participation, they will be asked to sign the Informed Consent Form (ICF) as approved by the reviewing Institutional Review Board. One copy of the completed Informed Consent Form will be given to the subject and the original must be retained as a source document. Subjects will be randomized only after informed consent has been obtained. A unique subject study ID will be assigned upon signature of Informed Consent. The subject study ID number will be recorded on all pertinent study records, as described in [Section 15.5](#) of this document

Subject discharge for the hospital is anticipated to occur on POD. At discharge the subject will be provided with a blood pressure cuff and be trained on "at home" blood pressure monitoring and recording. They will be instructed to undergo physical therapy and receive a document outlining the recommended content of that therapy. They will also be provided with a prescription for Study Medication which will be written in a blinded format for either losartan or placebo. Subjects will be instructed to visit the Vail Hospital Pharmacy to obtain the correct, blinded Study Medication. Study Medication Logs will be provided, with instructions for completion.

Subjects will also be provided with a prescription for a basic metabolic panel to be drawn by their local laboratory within 7-10 days post medication initiation.

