### **11.2 Day 2 Post-operative (No Visit Required)**

Subjects begin taking Study Medication

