### **11.3 Day 7-10 Post-operative (No Visit Required)**

Subjects visit their local laboratory and a Basic Metabolic Panel is drawn to include:

- Glucose;
- Calcium;
- Sodium;
- Potassium;
- Carbon Dioxide (CO2);
- Chloride;
- Blood Urea Nitrogen (BUN); and
- Creatinine.

In addition, each subject will be contacted by a Study Team member to confirm that the blood draw has occurred, and Study Medications are being logged. The occurrence of protocol deviations and all adverse events will be recorded.

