## **12.0 Study Management of Adverse Events**

### **12.1 Definition**

Adverse Event – An adverse event (AE) is any untoward medical occurrence in a subject administered a Study Medication and which does not necessarily have a causal relationship with this treatment. An AE can therefore be any unfavorable and unintended sign (including an abnormal laboratory finding), symptom, or disease temporally associated with the use of whether or not related to the Study Medication (ICH E2A II/A/1, 21 CFR 312.32).

All pre-existing medical conditions will be recorded on the medical history study document. Starting with the administration of the Study Medication any new experience that was not present at baseline or worsening of an event present at baseline in intensity or frequency, is considered an adverse event.

Note: Unchanged, chronic conditions are NOT adverse events and should not be recorded.

It is recognized that subjects will exhibit (throughout follow-up) symptoms of the underlying disease process of that fluctuates in severity and duration.

Adverse events will include those occurrences, which when compared to before treatment meets any of the following criteria:

- Represent a new event or escalation of an event;
- Require a new escalation in treatment;
- Lasts longer;
- Experienced more frequently;
- More intense;
- Different in character ( e.g. stabbing vs. ache);
- Experienced in a different part of the body; and/or
- Brought on by activity that previously did not cause the symptom.

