**Printed Name of Person Obtaining Consent**

## 23.2 Appendix B – Study Schemata

|  | Standard of Care Used for Screening | Visit 1
POD 1    | Telephone Contact        | Telephone Contact
Day 35 | Visit 2
3 months | Telephone Contact       | Telephone Contact        | Visit 3
18 Months |
|--|-------------------------------------|---------------------|--------------------------|-----------------------------|---------------------|-------------------------|--------------------------|----------------------|
| Window   |                                     | (or upon discharge) | 7-10 days post discharge | +/- 3 days                  | +/- 4 weeks         | 6 months
+/- 4 weeks | 12 months
+/- 8 Weeks |                      |
| I/E Criteria   | X                                   |                     |                          |                             |                     |                         |                          |                      |
| Vitals, H&P  | X                                   |                     |                          |                             | X                   |                         |                          |                      |
| BMI  | X                                   |                     |                          |                             |                     |                         |                          |                      |
| Demographic Info   | X                                   |                     |                          |                             |                     |                         |                          |                      |
| Medical History  | X                                   |                     |                          |                             | X                   |                         |                          |                      |
| Trauma Chronology  | X                                   |                     |                          |                             |                     |                         |                          |                      |
| Circumduction eval   | X                                   |                     |                          |                             | X                   |                         |                          |                      |

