| VAS  | X                                   |                     |                          |                             | X                   | X                       | X                        | X                    |
| Informed Consent   |                                     | X                   |                          |                             |                     |                         |                          |                      |
| Randomization  |                                     | X                   |                          |                             |                     |                         |                          |                      |
| Medication Pick -up  |                                     | X                   |                          |                             |                     |                         |                          |                      |
| Blood Pressure Cuff, Medication and BP Logs. PT instructions |                                     | X                   |                          |                             |                     |                         |                          |                      |
| Compliance Check   |                                     |                     | X                        | X                           |                     |                         |                          |                      |
| Protocol Deviations  |                                     |                     | X                        | X                           | X                   | X                       | X                        | X                    |
| Adverse Events   |                                     |                     | X                        | X                           | X*                  | X*                      | X*                       | X*                   |
| Basic Metabolic Panel  |                                     |                     | X                        |                             |                     |                         |                          |                      |

\*As related to the target hip only

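### The plan schedules one metabolic panel, on treatment, and records no pre-dose value, so a single subject's abnormal creatinine or potassium cannot be judged against a study baseline

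*Combined protocol and SAP*

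**What the plan says.** Section 11.1 (Visit 1, POD 1) hands each subject a "prescription for a basic metabolic panel to be drawn by their local laboratory within 7-10 days post medication initiation". Section 11.2 starts dosing on POD 2: "Subjects begin taking Study Medication". Section 11.3 places the draw at POD 7-10: "Subjects visit their local laboratory and a Basic Metabolic Panel is drawn to include" eight analytes, among them sodium, potassium, BUN and creatinine. In Appendix B the row "Basic Metabolic Panel" carries one mark, in the column timed "7-10 days post discharge". It is blank under screening and Visit 1.

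The pre-operative data in Section 11.0 cover demographics, history, co-morbidities, medication, hip examination, patient-reported outcomes and a T2 MRI. Of these it says: "These routine baseline measurements will be used to evaluate preliminary eligibility". No blood chemistry is listed there or under Screening Tools in the Synopsis. The general exclusions in Section 10.3.2 cover losartan use, allergy, interacting drugs and blood pressure ("Are hypotensive as confirmed by the surgical anesthesiologist"), but not renal function or potassium.

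Section 12.1 counts as an adverse event, once dosing has begun, "any new experience that was not present at baseline or worsening of an event present at baseline in intensity or frequency".

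**The concern.** Three rules in the plan turn on change within a subject. Section 12.1 asks whether a finding is new or worse than at baseline. The relatedness part of Section 12.2 asks the investigator to weigh timing and underlying disease. Section 14.3 makes acute renal failure, for subjects on losartan, a reason to stop the drug at once. For renal and electrolyte findings the plan collects one value, after dosing has started, so its own data hold nothing to compare it with.

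Safety is one of two primary objectives (Section 9.1), and occurrence of adverse events is a primary endpoint (Section 9.4). A misjudged renal event could blame the drug for impairment that was already there, or dismiss a real change as long-standing. If no sample was drawn before dosing, that value cannot be recovered afterwards.

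**Working it through.** The plan states no figure on this point to reproduce. The check sets the schedule beside the rules that would use it, with a little arithmetic.

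**Step 1. Does the draw always fall on treatment?** The window is worded three ways. Inputs: first dose on POD 2 (Section 11.2), twice-daily dosing for about one month (Section 6.0), discharge expected on POD 1 (Synopsis). Doses scheduled before the draw day = 2 × (draw POD − 2).

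| Source | Window counted from | Draw POD | Doses before draw day |
|---|---|---|---|
| Section 11.3 | surgery | 7 to 10 | 2 × 5 = 10 to 2 × 8 = 16 |
| Appendix B | discharge (POD 1) | 8 to 11 | 2 × 6 = 12 to 2 × 9 = 18 |
| Section 11.1 | first dose (POD 2) | 9 to 12 | 2 × 7 = 14 to 2 × 10 = 20 |

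Under every wording the subject is on treatment. Panels required before dosing: 0. Panels required on treatment: 1.

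**Step 2. Which judgments lack a comparator, and which of them can move a count?**

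| Judgment | Needs an earlier value? | Can it change the adverse event count? |
|---|---|---|
| New or worse than baseline (12.1) | Yes | Yes, it decides whether there is an event |
| Related to the drug (12.2) | Yes, to show that the change followed dosing | No, 12.2 records every event whatever its suspected cause |
| Renal failure is acute (14.3) | Yes | No, it governs dosing |
| Electrolyte imbalance is significant (14.3) | No, the absolute level suffices | No |

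Section 12.2 also says that a laboratory measurement should not itself be the event term. The point is therefore confined to abnormalities significant enough to be recorded as a diagnosis.

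**Step 3. Size of one changed new-or-worse judgment.** With 20 subjects per arm (Section 6.0), one event is 1/20 = 5%. For that event type the arm's rate moves from 0/20 = 0% (exact 95% CI 0 to 16.8%) to 1/20 = 5% (exact 95% CI 0.1 to 24.9%). The proportion of subjects with any adverse event moves only if that subject has no other recorded event.

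**Step 4. What one value leaves open (assumed values, for illustration).** Take a day 7-10 creatinine of 1.5 mg/dL.

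- Pre-dose 1.5: 1.5/1.5 − 1 = 0% rise.
- Pre-dose 1.0: 1.5/1.0 − 1 = 50% rise.
- Pre-dose 0.7: 1.5/0.7 − 1 = 114% rise.

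The same result fits stable impairment or a doubling. The documents give no rate of such abnormalities, so no expected number is calculated.

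**The case against.** The strongest reply is that the gap has little consequence. Several parts of it stand.

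- **Existing results.** Subjects come from the investigator's own practice (Section 10.2), have a pre-operative medical review (Section 11.0) and are seen by an anesthesiologist. A reader might infer that the investigator will have no earlier creatinine. The documents do not show that. They list what the study collects, not what the hospital tests. The supportable statement is that the plan does not require such a value to be recorded.
- **The stop decision.** A reader might infer that Section 14.3 cannot be applied without a baseline. It can: its third item lets the investigator remove a subject whose health, safety or welfare is at risk, so a worrying creatinine can be acted on without proof that it is acute. What stays unresolved is how to classify the event.
- **Low risk.** Subjects are 18-60 years old, the dose is 12.5 mg twice daily for a month, and Section 5.3 treats all antihypertensive drugs as excluded interacting medication. The rise in urea and creatinine cited there followed 100 mg, and that section reports no significant effects at 12.5 mg. The problem should be rare.
- **History and follow-up.** Medical history captures known renal disease, and Section 12.2 follows events to resolution or stability, which helps separate acute from chronic later. Neither supplies a creatinine or potassium value when the day 7-10 result arrives.
- **An imperfect baseline.** A POD 1 sample reflects recent surgery, and the later sample comes from a local laboratory. It can still separate large changes from none.

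**Conclusion.** The point holds in a limited form. The plan requires one panel, on treatment, and no pre-dose value. For an individual with a clinically significant day 7-10 abnormality, study data cannot settle whether it is new or worse, whether it followed dosing, or whether renal failure is acute.

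A reader might infer that the safety comparison is biased or that the overall adverse event rate is open to a 5-point error. The documents support neither. Both arms have the same single panel, so the randomized comparison of day 7-10 values stands. The 5 points apply to one event type and only through the new-or-worse judgment.

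This rests on the protocol sections and Appendix B as read; the consent form was not available for checking. It also assumes that no hospital result is transcribed informally. It is a cheap improvement to patient safety and event classification, not a flaw in a planned analysis.

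**What to change.** 1. In Appendix B and Section 11.1, record the latest routine perioperative basic metabolic panel as the study baseline. Where none exists, take one sample on POD 1, after consent and before the first dose on POD 2. Section 6.0 already has subjects collect medication before leaving hospital.
2. In Section 11.1, state that the investigator reviews and documents creatinine, potassium and sodium before dosing. If a value is clinically significant, the first dose is held until the abnormality is resolved or explained.
3. State that this value is the baseline for judging day 7-10 abnormalities under Sections 12.1 and 12.2, and for the acute renal failure criterion in Section 14.3.

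No new exclusion and no rule that turns out-of-range values into adverse events is needed.

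Cost: one mark in the table and a few sentences; at most one blood draw for each of 40 subjects, and none where a routine result exists; same-day reporting and review of any POD 1 sample; and an occasional delayed first dose. The text should add that small differences from a POD 1 value, taken just after surgery and in a different laboratory, are not to be read as drug effects.
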